12.2 Safety assessment

The safety variables will be analyzed in the Safety Populations, missing measurements will not be imputed.

Adverse events

Adverse events will be coded using the Medical Dictionary for Regulatory Activities (MedDRA, version 19).

Data on adverse events will be presented in terms of the number and proportion of patients with any adverse events overall, by system organ class (SOC) and preferred term (PT).

The number (proportion) of patients with AE and the number of AE will be tabulated by system organ class and preferred term, as well as by relationship to study treatment and severity. Within each system organ class and preferred term, each patient will be counted only once with the closest relationship to the study treatment or maximum severity. In the case of missing value of severity or relationship, the AE will be considered in the table as "severe" and "related", respectively.

The following tables will be provided:

- The number (proportion) of patients with AE and the number of AEs by system organ class and preferred term;
- The number (proportion) of patients with AE and the number of AEs related to study treatment by system organ class and preferred term;
- Number (proportion) of patients with AE and the number of AEs by severity, by system organ class and preferred term;
- The number (proportion) of patients with AE and the number of AEs that led to discontinuation of the program (for the active group), by system organ class and preferred term;
- The number (proportion) of patients with AE and the number of AEs that are fatal, by system organ class and preferred term;
- The number (proportion) of patients with SAE and the number of SAE, by system organ class and preferred term;

The analysis will not include AEs that started before the start of a lifestyle change program for patients in the active group. In the case of a partial start date for AE, it will be compared as far as possible with the program start date to determine if it occurred prior to the start of the program. If the available information is not sufficient, the AE will be considered to have started after the beginning of the program.

The analysis of the SAE will include all registered SAE. Data on all AE / SAE will be presented in the form of listings.

Laboratory data

Laboratory investigations were conducted on Visit 1, Week 12 and 48 and included the following parameters:

Biochemistry: total protein (g/l), cholesterol, LDL, HDL (mmol/L), triglycerides (mmol/L), ALT (U/l), AST (U/l), CPK (U/l), creatinine ($\mu\text{mol/L}$), GFR.

Haematology: hemoglobin (g/l), leukocytes ($10^9/l$) (+ formula), erythrocytes ($10^{12}/l$), platelets ($10^9/l$), ESR.

Urinalysis: color, transparency, relative density, protein, glucose, ketones.

Descriptive statistics will be used to analyze the laboratory data. Hematology and biochemistry lab parameters values and their absolute changes from baseline will be presented by groups and study visits. Tables of shifts relative to normal ranges (low / normal / high) will be tabulated by visit. For the urinalysis parameters, the number and proportion of the normal / non-clinically significant deviations / clinically significant deviations will be tabulated. All laboratory data will be presented in listings.

Vital signs

Systolic and diastolic pressure (mmHg), heart rate and respiratory rate will be recorded at each visit of the study. For the analysis of vital signs, descriptive statistics will be used. Parameters of blood pressure, heart rate and respiratory rate and their absolute changes in from baseline values will be tabulated by visit. All vital signs data will be presented in listings.

ECG

ECG was performed on Visit 1, Week 12 and 48. The ECG results (normal / non-clinically significant deviations / clinically significant deviations) will be tabulated as the number and percentage of patients with each of the assessments from the number of patients present at the visit.

Physical examination

The results of the physical examination, including an overall assessment of the basic parameters of the vital activity of the organism, will be recorded on Visit 1 and on all visits, beginning from Week 12 in both groups, and also 4 and 8 weeks after inclusion in the study for active group patients. The results of the physical examination will be tabulated as the number and percentage of patients with each of the assessments (normal / non-clinically significant deviations / clinically significant deviations) from the number of patients present at the visit.

13 Other variables

The scale of individual perception of physical activity (the Borg scale) was filled on Visit 1 and at the end of the program in the active group. The score on the scale will be presented using descriptive statistics as the number and proportion of patients for each category. Changes will be presented as cross-tabulation of estimates at the beginning and after the program.

The questionnaire for hypoglycemia evaluation was filled on Visits 1, 24 and 48 weeks of observation. For each patient, the result for subscales 4, 5, 6, 7, 8, 9 will be calculated as the mean value of answers to subscale questions. The results for all subscales and changes from baseline will be presented descriptively by groups and visits.

14 Interim analysis

Not planned.

15 Presentation of results

Statistical analysis will be performed using IBM® SPSS® Statistics Version 19.0 or later. All results will be presented in the form of tables, listings and figures.

16 Changes in the statistical analysis plan

The analysis of the quantitative efficacy endpoints at each individual assessment visit using ANCOVA was replaced with an analysis based on a similar model, which takes into account the correlation between the repeated measurements, using the GEE method (Generalized Estimating Equations).

Secondary dichotomous endpoints - a decrease of HbA1c level by at least 0.5% from baseline, achievement of HbA1c $\leq 7\%$ by 12 months of observation, a decrease in SBP and DBP by at least 5 mmHg at 3, 6, 9, 12 months of observation - will also be analyzed using GEE (logistic regression of repeated changes) instead of logistic regression for individual evaluation visits.

17 References

1. ICH (1998). International Conference on Harmonization. Guideline E9 on Statistical Principles for Clinical Trials.

18 List of results

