The full study lasts 12 months. Patients in active group are monitored intensely every 7 days. After first 13 weeks assessment of weight and health condition are conducted on a monthly basis (see Table 7.1 as reference). For patients in control group all examinations should be conducted every three months (see Table 7.2 as reference).

In order to collect data for the primary and secondary end points (6.3, 6.4) in control group assessment of all indicators will be conducted at trial' start and then the patients will be invited to the doctor by the end of 3rd, 6th, 9th and 12th months (see table 7-2).

Patients from active group fill out the Information card before they enter the study (**Appendix 8**) and Registration form (**Appendix 9**). Patients fill out the Information card at the end of the study as well (including assessment of individual perception of physical exercises using the scale of Borg).

It is necessary to discuss with a patient the patient's ability and readiness to make changes in his/her lifestyle when a doctor makes a decision to include a patient in the study.

The program of active weight reduction includes group classes with the team of doctors:

- Nutritionist in regards to healthy nutrition (**Appendix 10**)
- TE doctor/fitness trainer in regards to physical activity (**Appendix 11**)
- Psychologist in regards to motivation and education (**Appendix 12**) and self-control (**Appendix 13**)
- Endocrinologist (**Appendix 13**).

Classes for the patients in active group are conducted one time a week in the first 12 weeks with the following monitoring once a month in the next 36 weeks. Total period of observation is one year (48 weeks). Detailed classes description is in the **Appendix 1**.

Patients from control group do not take part in the group classes but their indicators are collected during the routine visits to doctors (a doctor will invite a patients following the plan of visits, table 7-2).

All prescribed procedures assigned by the doctors should meet the medical needs of the patients and should be conducted according to the recommendations of the Russia Association of Endocrinologists.

The specialists will use their professional skills in order to achieve the purposes and outcomes and they are responsible for taking into account the guidelines of the RAE.

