10.5.2 Hypoglycemia Perspectives Questionnaire

The impact of T2DM on various aspects of patient's health-related quality of life will be assessed by the following validated instruments, each of which will be performed as indicated in Table 7-1 and Table 7-2.

- Health Questionnaire EQ-5D-3L
- Hypoglycemia Perspectives Questionnaire
- DTSQ

Doctor (investigator or acting as investigator) should fill out this survey based on what the patient says. The survey will be filled out in Russian before the patient attends the 1st visit of the study. The doctor should ask the patient to answer the questions and fill out the survey. The originals should be kept with other primary documents in the research center.

The patient should fill out the Diary of self-control in between the visits. The diary has teared-off pages where all data on food intake, the level of glucose before and 2 hours after the food intake and hypoglycemia therapy should be mentioned. Additionally, the patient should register in the Diary the change in glucose level, BP and pulse before and after physical exercises. Completed pages should be given to the doctor by the patient at each visit. In case of AEs or SAEs they should be registered according to the instructions of the Chapter 11. Reporting system is also described in Chapter 11.

11 Safety monitoring

Any serious adverse events will be reported to the Local Ethics Committee within 24 hours of the occurrence. All serious adverse events will also be reported to Novartis Drug Safety & Epidemiology (DS&E) within 24 hours of the investigator (or designee) being aware of the serious adverse event. Specific definitions of adverse events, and serious adverse events, are outlined below, along with reporting criteria required by Novartis.

Adverse events (AE)

Information about all AEs, whether volunteered by the patient, discovered by investigator questioning, or detected through physical examination, laboratory test or other means, will be collected and recorded on an Adverse Event Case Report Form and will be followed up as appropriate.

An AE is any undesirable sign, symptom or medical condition occurring after starting study treatment, even if the event is not considered to be part of lifestyle changes implied by this study.

Medical conditions/diseases present before starting study treatment will only be considered adverse events if they worsen after starting study treatment (any procedures specified in the

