12.3 Database management and quality control

Novartis staff, or CRO working on behalf of Novartis, review the data entered into the eCRF by investigational staff for completeness and accuracy and instruct the site personnel to make any required corrections or additions.

Queries are sent to the investigational site using an electronic data query. Designated investigator site staff is required to respond to the query and confirm or correct the data.

Concomitant medications entered into the database will be coded using the World Health Organization (WHO) Drug Reference List, which employs the Anatomical Therapeutic Chemical classification system.

Medical history and AEs will be coded using the Medical Dictionary for Regulatory Activities (MedDRA) terminology.

13 Data analysis

Descriptive statistics will be applied in the study to describe the sample size of the patients at baseline and at follow-up visits, demographic data recorded during the examination of the study parameters, as well as their changes.

The choice of parametric or non-parametric criteria for testing statistical hypotheses will be determined on the basis of the Kolmogorov-Smirnov criteria (conclusion of the presence or absence of statistically significant differences between the distribution of the respective parameter and the normal one), as well as with the graphical methods.

AE data will be presented as an absolute number and as the proportion of the patients with any AE, according to the organ systems and specific AE with corresponding 95% confidence intervals (CI). The association between therapy duration and AE (SAE) risk will be analyzed on the basis of the proportional-hazards regression model of the survival analysis. Age, sex, BMI, disease duration, baseline HbA1c, will be taken into account in the model for the control of potential confounding factors. Secondary indicators will be analyzed the same way.

The primary analysis of the proportion of the patients with response on the treatment will be performed using multivariate logistic regression and calculating odds ratios with

corresponding 95% CI. To control the potential confounding factors, age, sex, BMI, disease duration, the baseline values of HbA1c will be taken into account in the regression model.

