6.2 Exclusion criteria

Patients fulfilling any of the following criteria are not eligible for inclusion in this study:

1. Pregnant or nursing (lactating) women, where pregnancy is defined as the state of a female after conception and until the termination of gestation.
2. Type 1 diabetes
3. Proliferative retinopathy, hemorrhage and disinsertion of retina
4. Renal impairment: serum creatinine >1.5 mg/dL, creatinine clearance < 40 ml/min and/or proteinuria.
5. The lack of ability to perform the physical exercises due to the orthopedic or cardiovascular disorders *
6. Chronic alcoholism, acute alcoholic intoxication

* - the criterion is applicable only for the active group.

7 Population determination for statistical analysis

- All enrolled patients: all patients who signed informed consent for inclusion in the study. The population will be used for the disposition data summaries and listings.
- Safety Population: all patients of the active group included in the study, who started participating in the lifestyle correction program, and all patients of the

control group for whom the observation was started. The population will be used to summarize adverse events and other safety parameters.

- Full Analysis Set (FAS): all patients who provided baseline data and data to evaluate at least one efficacy parameter after the onset of observation. The population will be used for efficacy analyses.
- Per Protocol Set (PP): all FAS patients who did not have any major protocol deviations. The population was used to analyze the primary endpoint (sensitivity analysis).

The patient can be excluded from the Per Protocol Set for the following reasons:

- did not attend more than 3 consecutive classes in the active group;
- missed at least 50% classes of the program;
- did not provide data for the estimation of the primary endpoint.

8 General considerations

The latest available estimates before the start of the program for the active group and data from the Visit 1 for the control group will be used as the baseline values for the analysis of quantitative efficacy and safety parameters. The baseline visit is Visit 2 (Week 1) for the active group and Visit 1 for the control group.

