Table 4.3.5 Analysis of changes in WHR compared to baseline values (FAS)

Table 4.4.1 Descriptive statistics for HbA1c values and their changes in percent and absolute units by study visits (FAS)

Table 4.4.2 Analysis of absolute changes of HbA1c compared to baseline values at 3, 6, 9 and 12 months of observation (FAS)

Table 4.4.3 Analysis of changes in HbA1c in % compared to baseline values at 3, 6, 9 and 12 months of observation (FAS)

Table 4.4.4. Reduction of HbA1c level by at least 0.5% of baseline by study visits (FAS)

Table 4.4.5 Analysis of the reduction in HbA1c level by at least 0.5% from baseline (FAS)

Table 4.4.6 Analysis of the achievement of HbA1c \leq 7% at 12 months of observation (FAS)

Table 4.4.7 Descriptive statistics for FBG values and their changes in percent and absolute units by study visits (FAS)

Table 4.4.8 Analysis of the absolute changes in FBG compared to the baseline values at 3, 6, 9 and 12 months of observation (FAS)

Table 4.4.9 Analysis of FBG changes in % compared to baseline values at 3, 6, 9 and 12 months of observation (FAS)

Table 4.5.1 - 4.5.2 Descriptive statistics for values of SBP and DBP and their changes in absolute units by study visits (FAS)

Table 4.5.3 - 4.5.4 Analysis of absolute changes in SBP and DBP compared to baseline values at 3, 6, 9 and 12 months of observation (FAS)

Table 4.5.6 - 4.5.8 Decrease in SBP and DBP by at least 5 mmHg from baseline (FAS)

Table 4.5.9 - 4.5.10 Analysis of the decrease in SBP and DBP by at least 5 mmHg from baseline by study visits (FAS)

Table 4.6.1 - 4.6.4 Descriptive statistics for lipid profile values (cholesterol, triglycerides, LDL, HDL) and their changes in percent and absolute units for study visits (FAS)

Table 4.7.1 - 4.7.4 Analysis of changes in % of lipid profile (cholesterol, triglycerides, LDL, HDL) compared to baseline values at 3 and 12 months of observation (FAS)

Table 4.8.1 - 4.8.4 Analysis of absolute changes in lipid profile (cholesterol, triglycerides, LDL, HDL) compared to baseline values at 3 and 12 months of observation (FAS)

Table 5.1.1 Frequency table for adverse events (Safety Population)

Table 5.1.2 Frequency table for adverse events by severity (Safety Population)

Table 5.1.3 Frequency table for adverse events by relationship to study treatment (Safety Population)

Table 5.1.4 Frequency table for adverse events leading to discontinuation (Safety Population)

Table 5.1.5 Frequency table for fatal adverse events (Safety Population)

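### AE tables give crude percentages without the protocol's 95% CIs or time-based analysis, so a group difference or similarity cannot be separated from contact frequency (21 v 4) and shorter active follow-up

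*SAP*

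**What the plan says.** **Summary measure.** SAP 12.2 states: "Data on adverse events will be presented in terms of the number and proportion of patients with any adverse events overall". It adds breakdowns by system organ class, preferred term, severity and relationship. The output list has frequency tables only (Tables 5.1.1 to 5.1.5 and 5.2.1). It has no interval, patient-time or time-to-event output for AEs, and no between-group AE test.

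**What the protocol promised.** Protocol 13 has AE proportions by organ system and "specific AE with corresponding 95% confidence intervals (CI"). It also has a proportional-hazards model relating therapy duration to AE and SAE risk, adjusted for baseline covariates.

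**Counting window.** For the active group SAP 12.2 says: "The analysis will not include AEs that started before the start of a lifestyle change program for patients in the active group". There is no counterpart for controls. For serious events it says: "The analysis of the SAE will include all registered SAE". SAP 8 says: "The baseline visit is Visit 2 (Week 1) for the active group and Visit 1 for the control group".

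**Contacts.** The footnote to the active-group schedule in Protocol 7 has weekly visits 2 to 13 and monthly visits 14 to 22. For the other group, Protocol 10 says: "For patients in control group all examinations should be conducted every three months".

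**Follow-up.** Protocol 8 and SAP 6 expect about 20% drop-out. They define it only for the active group (three consecutive missed classes in the first 12 weeks) and expect none in controls.

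**The concern.** The AE tables will put two columns of percentages next to each other, and readers will compare them whether or not a test is planned. The columns differ in how often patients are seen and in how long they are followed. More contacts tend to raise the recorded active percentage. Drop-out and a slightly later counting start tend to lower it. An apparent excess in the programme group may be an effect of closer observation, and an apparent similarity may hide a real excess.

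The tools that would limit misreading are missing. Without intervals, a zero in 30 controls can be taken for absence of risk. Without patient-time, unequal follow-up stays inside the percentage. The protocol had committed to intervals and to a time-based analysis, and a reader of the SAP cannot tell whether leaving them out was intended.

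**Working it through.** Neither document states an AE rate, a detection probability or a planned AE precision, so there is no AE figure to reproduce. The sample size of 100 + 30 concerns weight, and nothing here depends on it.

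**1. Contacts after Visit 1.** Active: visits 2–13 = 12, visits 14–22 = 9, total 21. Control: ends of months 3, 6, 9 and 12 = 4. Up to week 12 this is 12 v 1, and afterwards 9 v 3. Table 7-2 is not in the available text, so the control count rests on Protocol 10.

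**2. Counted time.** Inputs: 48 weeks planned; active counting from week 1 (taking Visit 1 as week 0); 20% of active patients leaving at week *d* (assumed 4 to 12, because the rule covers only the first 12 weeks); no control drop-out.

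Mean active weeks = 0.8 × (48 − 1) + 0.2 × (*d* − 1)
- *d* = 4: 37.6 + 0.6 = 38.2; 38.2/48 = 0.80
- *d* = 8: 37.6 + 1.4 = 39.0; 39.0/48 = 0.81
- *d* = 12: 37.6 + 2.2 = 39.8; 39.8/48 = 0.83

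**3. Net bias with equal true rates.** Two simple models, both assumptions, with active drop-out at week 8.

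*Look-back model:* an event is recorded only if it occurred within *w* weeks before a contact, counting from week 0. Completers' covered weeks are 30 (*w* = 2) or 48 (*w* ≥ 4). Those who leave at week 8 have 8. Controls have 4 × *w*, up to 48.

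| *w* | Active weeks | Control weeks | Ratio |
|---|---|---|---|
| 2 | 0.8×30 + 0.2×8 = 25.6 | 8 | 3.2 |
| 4 | 0.8×48 + 0.2×8 = 40 | 16 | 2.5 |
| 8 | 40 | 32 | 1.25 |
| 12 | 40 | 48 | 0.83 |

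*Recall model:* the chance of recording an event at the next visit decays with half-life *h*, counting active events from week 1. An interval of *g* weeks contributes τ(1 − e^(−*g*/τ)) effective weeks, with τ = *h*/ln 2.

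| *h* (weeks) | Active | Control | Ratio |
|---|---|---|---|
| full recall | 39.0 | 48 | 0.81 |
| 26 | 37.4 | 41.1 | 0.91 |
| 12 | 35.6 | 34.6 | 1.03 |
| 8 | 34.1 | 29.8 | 1.14 |
| 4 | 30.1 | 20.2 | 1.49 |
| 2 | 24.2 | 11.4 | 2.13 |

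At a true rate of 1 AE per 48 weeks in both groups, patients with any recorded AE would be 52.7% active v 63.2% control under full recall, and 38.4% v 21.1% with a 2-week half-life. The same truth produces a deficit or an excess.

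**4. Precision.** The exact two-sided 95% upper limit for 0/30 is 1 − 0.025^(1/30) = 11.6%. An observed 30% has exact limits of 14.7% to 49.4% in 30 patients and 21.2% to 40.0% in 100. The difference has an approximate half-width of 1.96 × √[0.3 × 0.7 × (1/100 + 1/30)] = 18.7 points.

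**5. Windows.** Take an active patient with an SAE that starts between Visit 1 and the first class, who then starts the programme. The event enters Table 5.2.1 but not Table 5.1.1, nor Table 5.1.5 if it later proves fatal. The tables do not say that their windows differ.

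**The case against.** Much of the opposing case is sound.

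- **No AE contrast is planned.** The SAP only tabulates AEs, and they are not among the objectives or endpoints. A reader might infer a formal comparison, but the documents contain none. What remains is the side-by-side display.
- **Ascertainment is not shown to dominate.** A reader might infer from 21 v 4 that any AE difference mainly reflects how often patients were asked. The documents do not support that. They give no AE or detection rates, the biases oppose each other, and the ratio falls below 1 when recall is good. SAEs must also be reported within 24 hours of awareness, so they depend less on scheduled contact.
- **The active-group cut can be defended.** Protocol 11 says pre-existing conditions count if they "worsen after starting study treatment (any procedures specified in the" protocol), which might suggest counting from Visit 1. But Protocol 10.3 places baseline assessments before first study treatment. Protocol 11 also sends non-serious events between consent and treatment start to the medical history form, while SAEs are reportable from consent. The SAP rule fits that reading, and the difference is about 1 week in 48. Only the unwritten control start and the unlabelled SAE window remain.
- **SAEs in patients who never start are not lost.** SAP 7 assigns listings to all enrolled patients, and SAP 12.2 lists all AEs and SAEs.
- **Exposure is visible.** Table 3.1 shows duration of participation. It is not linked to the AE tables, however.
- **SAP 16 may not be the place to look.** It appears to log changes to the analysis plan itself, since the ANCOVA it replaces is not in Protocol 13. In that case the dropped AE analyses are recorded nowhere.
- **The hazards model would not cure the imbalance.** It concerned therapy duration and named no group term. Neither it nor the CIs would correct for 21 v 4 contacts.

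**Conclusion.** The point holds in a limited form. SAP 12.2 reports AEs as crude counts and proportions and omits, without explanation, the 95% CIs and proportional-hazards analysis stated in Protocol 13. With 21 v 4 scheduled contacts and counted active time about 0.80 to 0.83 of control time, neither a difference nor a similarity in AE percentages can be separated from ascertainment and follow-up. With equal true rates, the active-to-control ratio of recorded events is about 0.8 to 3.2, so the direction of bias is unknown.

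The contact counts come from the documents. The time ratio assumes that 20% of the active group leaves at weeks 4 to 12. The bias range also rests on the assumed look-back windows and recall half-lives. The 11.6% limit for 0/30 needs only a binomial model. The primary endpoint is not affected. This is an inexpensive improvement to safety reporting, not a flaw that invalidates the safety data.

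**What to change.** In SAP 12.2 and Tables 5.1.1 to 5.2.1:

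1. Restore 95% CIs, exact, for the proportions of patients with AEs and SAEs in each group.
2. Add AEs and SAEs per 100 patient-years, using the participation time already derived in SAP 11. Numerator and denominator must cover the same window, so SAEs outside participation time stay in the counts but not in the rate.
3. State the AE counting start for controls (Visit 1, the SAP's own baseline). Footnote that the SAE table uses a wider window than the AE and fatal-AE tables, or put the fatal-AE table on the SAE window.
4. State that non-serious AE frequencies are descriptive because scheduled contacts were 21 v 4, and rest between-group safety statements mainly on SAEs.
5. Either keep the protocol's proportional-hazards analysis or record its removal, with the reason, as a change from the protocol.

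AEs ongoing at the visits both groups share (weeks 12, 24, 36 and 48) could be an optional supplement. That is a prevalence measure and misses short events, so it should not be the sole basis for between-group statements.

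The cost is SAP wording and a few table columns, with no new data. Intervals in 30 controls will be wide, and patient-time corrects for follow-up but not for contact frequency.
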